1.7 Drugs/Devices/Biologics

■ N/A

1.8 Primary Specimen Collection

A. What types of specimen will be collected, where, and by whom?

We will utilize a urine or saliva screen that tests for buprenorphine and methadone (to provide corroboration of MAT engagement and compliance) and additional substances (e.g., benzodiazepines, barbiturates, cocaine, marijuana, methamphetamine, morphine, oxycodone, phencyclidine and amphetamine). These specimens will be collected at baseline and each follow-up time point (8- and 16-weeks). Biochemical verification of self-report opioid relapse and other drug use is the gold standard measurement of drug use and, without biochemical verification, self-reported drug use as an outcome variable will be questioned by the scientific community. Participants will be mailed a urine or saliva test prior to the interview. Alternatively, the patient can pick up urine or saliva test at their respective clinic. If feasible, drug screen may be done in-person. At the time of the interview, participants will be instructed on how to administer the test and will be instructed to show the research assistant the results on the video conference. The research assistant will then record the results. If participants are unable or unwilling to attend a video research appointment, a research assistant will conduct an interview over the phone and participant will self-report the drug screen results. The fact that drug screen results are self-reported will be noted. Alternatively, if feasible, the drug screen may be done in-person. All results (positive or negative) be will be recorded in the research database that will only be identified with participant's study ID and not the participant's name. Drug test results will not be shared with anyone, including the participant's clinic, without written consent from the participant. With participant consent, the results of the most recent drug tests conducted by the patients' clinics may be obtained from the patients' charts.

8

B. How will the specimens be transported and by whom?

Version Number: 15, 2/2/2022 Protocol Number: Pro20190016877 PI Name: [name]

Protocol Title: Mindfulness Oriented Recovery Enhancement (MORE) as an Adjunct to Methadone Treatment RESERVED FOR IRB STAMP DO NOT MODIFY THIS SPACE

The sample will be collected by the participant and results read by research staff at the time of sample collection. The sample will be disposed as soon as results are read (typically within 10 minutes of sample collection) and recorded. The sample will not be transported.

C. Who will process the specimens?

Participants will be mailed a urine or saliva test prior to the interview. Alternatively, the patient can pick up urine or saliva test at their respective clinic. At the time of the interview, participants will be instructed on how to administer the test and will be instructed to show the research assistant the results on the video conference. The research assistant will then record the results. If participants are unable or unwilling to attend a video research appointment, a research assistant will conduct an interview over the phone and participant will self-report the drug screen results. Alternatively a drug screen can be done in-person. In this case, the participant will collect the specimen and the research staff will read the results directly, in person.

D. How long will the specimens be kept?

The sample will be disposed of immediately after results are read and recorded.

- E. How will the specimens be destroyed upon study completion?

 Samples will be flushed down the toilet (urine test) or disposed of in the trash (saliva test).
- F. If specimens will be banked for future use, what will be the process for providing investigators with access to the bank and how will this be tracked?

 N/A

1.9 Interviews, Focus Groups, or Surveys

A. Administration

Timing and Frequency

Research staff will collect interview data and drug screens from both intervention and control group subjects through video, phone interview, or in-person using standardized measures conducted at baseline and 8- and 16-weeks. Cognitive testing data will be collected at baseline and 8-weeks. If the research assessments are conducted over the phone, drug screen results will be recorded as self-reported. Additionally, subjects will engage in twice-daily EMA assessments of approximately 3-5 minutes each for 16-weeks. For 16-weeks, subjects will also initiate EMA communications to report lapses or serious cravings, which will also last for under 5 minutes. For those who do not complete their EMA, our research staff will do a timeline follow-back over the phone or video conferencing to collect missing EMA drug use data. EMA completion reports will be reviewed, weekly, and participants will be contacted, as needed, to collect missing daily drug use data.

Location

The assessments and drug screens will take place via video/online, phone interview, at their clinic, or at another safe and private location in the community (e.g., library, park, or coffee shop).

Procedures for Audio and Visual Recording

Audio or video recordings will be made of the MORE therapy sessions. All recordings will be stored in password protected computers, in a locked office at [name], or in password protected files, on the Rutgers network or HIPAA compliant Box file.

9

B. Study Instruments

Version Number: 15, 2/2/2022 Protocol Number: Pro20190016877 PI Name: [name]

Protocol Title: Mindfulness Oriented Recovery Enhancement (MORE) as an Adjunct to Methadone Treatment RESERVED FOR IRB STAMP
DO NOT MODIFY THIS SPACE

- Time until first opioid lapse assessed through ecological momentary assessment data and timeline follow-back.
- Time until MMT dropout assessed through clinic records (abstracted by the study counselor who will have access to the clinic records). Time until dropout will be calculated from enrollment until last dose of methadone.
- Total days of methadone treatment assessed through clinic records (abstracted by the study counselor who will
 have access to the clinic records). Number of days will be calculated from enrollment until each follow-up timepoint.
- Total days of opioid or any drug use assessed through EMA data and timeline follow-back
- Trajectories of positive and negative affect assessed through Positive and Negative Affect Schedule.
- Drug craving assessed with an adapted version of the Penn Alcohol Rating Scale.
- Pain severity and pain interference assessed with the Brief Pain Inventory and the Gracely Pain scale⁷

Assessment of additional secondary outcome and other relevant measures that could mediate or moderate outcomes are described below:

Ecological Momentary Assessmenet (EMA) data collection (ongoing from baseline to 16 weeks). The EMA and other survey data will be programmed as a REDCap or Qualtrics survey delivered over a password-protected smart phone, computer, or tablet that will not store any data. REDCap and Qualtrics are secure, HIPPA-compliant, webbased application for building and managing online surveys and databases. The EMA survey approach will involve 1) collecting event-contingent records of lapses when they occur as well as 2) regular random assessments, prompted by random text messages initiated by Twilio, 3x daily via smartphones. For event-contingent records, participants will be asked to initiate an entry when an opioid lapse or opioid craving without use occurs, and note how they were feeling and the extent of craving. One random assessment probe will be scheduled early in the day and one will be scheduled in the evening. The random probes will be generated by an algorithm in REDCap or Qualtrics and linked to a Twilio phone number. For random assessments, participants will be asked to note how they are feeling, drug use, and whether they completed their homework (if in the intervention group). Research staff will demonstrate to study participants how to use the phones/tablets, respond to the prompts, and provide event contingent data. Research staff will provide instructions about how to use the phone/tablet and practice using the phone/tablet with participants until they are capable of using it.

Data will be received by the REDCAP or Qualtrics system. Data access between the REDCap and Qualtrics databases and the web servers aew encrypted and restricted to a monitored port. All REDCap and Qualtrics data, which is displayed or captured by the user interface, is encrypted for security. Within REDCap and Qualtrics all data transactions including inserts, updates, deletions, import/export and reporting are logged. The EMA system in this study deployed via REDCap and Qualtrics will reside in a HIPAA compliant protected space. The REDCap and Qualtrics production and development servers use encrypted drives. Physical hardware will be secured in a locked facility.

The data will only be accessible to study investigators and staff. The data will be processed by an already developed REDCap or Qualtrics program that formats the data as a "long file" with one row per time point per individual participant. The investigators will employ linear mixed models to test the effects of MORE vs. the control condition on substance use, craving, pain, and other study variables. The treatment X time interaction will be the main fixed effect of interest. Models will include a random intercept, as well as a random slope if warranted by model fit statistics. Auto-correlation between repeated measures will be modeled as a first-order autoregressive function. We will also compute within-group linear mixed models examining mindfulness practice duration as a predictor of clinical outcomes.

EMA completion reports will be reviewed, weekly, and, as needed (at a maximum weekly), we will conduct a timeline follow-back⁹ with each participant to account for missing EMA drug use data. The timeline follow-back is a

10

Version Number: 15, 2/2/2022 Protocol Number: Pro20190016877 PI Name: [name]

Protocol Title: Mindfulness Oriented Recovery Enhancement (MORE) as an Adjunct to Methadone Treatment RESERVED FOR IRB STAMP DO NOT MODIFY THIS SPACE

reliable and valid measure where participants are asked to recall and record events (e.g., drug use) within a specified time period on a calendar.

Substance use history (Baseline). We will use the PhenX Toolkit-Substance Abuse and Addictions Core Tier 1 Collection⁸ to gather self-report information on lifetime use of opiates, alcohol, tobacco and substances, and past-30 day use of all substances.

Current substance use (Baseline, 8- and 16-- weeks). We will utilize a urine or saliva screen that tests for buprenorphine and methadone (to provide corroboration of MAT engagement and compliance) and additional substances (e.g., benzodiazepines, barbiturates, cocaine, marijuana, methamphetamine, morphine, oxycodone, phencyclidine and amphetamine). Participants will also be asked about overall number of days of use in the past 30 with questions based on PhenX Toolkit-Substance Abuse and Addictions Core Tier 1 Collection. For those prescribed opioids for pain, misuse will be assessed with the Current Opioid Misuse Measure. Drug test results conducted by the clinic during the study period will be obtained from participants' clinic charts. We will combine self-reports of opioid relapse and other drug use with biochemical measures because it is the gold standard, and without biochemical verification, self-reported drug use as an outcome variable will be questioned by the scientific community. If a biochemical measure is negative, but the participant reports drug use, the participant will be coded as using drugs since the biochemical measure will only capture a specific time point. However, if the participant self-reports drug abstinence, but the biochemical measure is positive for drug use (the more likely scenario) the participant will be coded as having used drugs.

Craving (Baseline, 8- and 16-- weeks). Opioid and other drug craving will be assessed with an adapted version of the Penn Alcohol Craving Scale (PACS)¹⁰ and the Craving Suppression Scale. The PACS is a valid, reliable, and internally consistent measure that consists of five self-report items that have been found to predict relapse. The items assess the intensity, frequency, ability to resist, and duration of craving. Originally developed to assess alcohol craving, it has been adapted and used to measure craving for various substances, including opioids,¹¹ and adapted versions have been used in trials of mindfulness-based interventions for substance use.¹² The Craving Suppression Scale is a 17 –item measure that assesses how individuals cope with craving

Pain (Baseline, 8- and 16-- weeks). For study eligibility, pain intensity will be assessed at baseline only with Gracely Box Scale, 13 a visual analog scale that ranges from 0 (no pain) to 20 (extremely intense pain). At baseline and both follow-up points, pain severity will also be measured with the Brief Pain Inventory (BPI; α = .87) a well-validated measure that has been widely used to tap acute and chronic pain. Participants will be asked to report their worst pain during the past week, least pain during the past week, average pain, and current pain. Response options range from 0 (no pain) to 10 (pain as bad as I can imagine). An overall pain severity score will be computed by taking the mean of the four items. Pain will also be assessed with the Sensations Body Map.

Pain interference (Baseline, 8- and 16-- weeks). Pain-related functional interference will be assessed with the pain interference subscale of the BPI⁷ (α = .88). Subjects will be asked to rate on a 0 (does not interfere) to 10 (completely interferes) scale the extent to which pain interfered with each of seven domains of normal functioning in the past week, including: general activity, mood, walking ability, normal work, relations with other people, sleep and enjoyment of life. An overall pain interference score will be computed by taking the mean of the seven items.

Coping with pain (Baseline, 8- and 16-- weeks). Cognitive coping with pain by reinterpreting painful sensations as innocuous sensory experiences will be assessed via the reinterpreting pain sensations subscale of the Coping Strategies Questionnaire¹⁴ (CSQ). This subscale has good internal consistency (α = 0.88) and is comprised of 6 items including "I don't think of it as pain but rather as a dull or warm feeling," and "I just think of it as another sensation such as numbness." Participants will be asked to report how much they generally engaged in this form of coping when they felt pain. Responses are rated on a scale ranging from 0 (never) to 6 (always); a reinterpretation of pain sensations total score can be obtained by adding up the four items (range: from 0 to 36). Scores on this scale are

Version Number: 15, 2/2/2022 Protocol Number: Pro20190016877

PI Name: [name]

Protocol Title: Mindfulness Oriented Recovery Enhancement (MORE) as an Adjunct to Methadone Treatment RESERVED FOR IRB STAMP DO NOT MODIFY THIS SPACE

meaningfully related to measures of pain and adjustment to pain, ¹⁴ and have been shown to mediate the therapeutic effects of mindfulness training on chronic pain. ¹⁵

Nonreactivity (Baseline, 8- and 16-- weeks). Nonreactivity to distressing thoughts and emotions will be measured with the Five Facet Mindfulness Questionnaire. This scale is comprised of items such as "When I have distressing thoughts or images, I 'step back' and I am aware of the thought or image without getting taken over by it." These skills appear to tap metacognitive decentering or disengagement from aversive experiences, and have been shown to mediate the effects of mindfulness training on decreased pain. 15

Reappraisal (Baseline, 8- and 16-- weeks). Reappraisal will be measured with the positive reappraisal subscale of the Cognitive Emotion Regulation Questionnaire (CERQ),¹⁷ an internally-consistent subscale (α = .85) which asks the respondent how often they "think I can become a stronger person as a result of what has happened" or "look for positive sides to the matter" to cope with stressful events. Responses are rated on a scale ranging from 1 (almost never) to 5 (almost always). In prior research, scores on this reappraisal scale were prospectively predictive of lower levels of future affective symptoms,¹⁷ and changes in CERQ reappraisal scores mediated the stress-reductive effects of mindfulness.¹⁸ Also reappraisal will be assessed with the 9-item Mindful Reappraisal Of Of Painful Sensations Scale. Responses are rated on a scale ranging from 0 (never do that) to 6 (always do that);

Positive and Negative Affect (Baseline, 8- and 16-- weeks). We will assess positive and negative affect with the valid and reliable Positive and Negative Affect Schedule (PANAS). The PANAS is a 20-item, self-report measure that consists of two scales (positive affect and negative affect) of 10-items each. Participants will rate factors related to positive or negative affect on a scale from 1 (not at all) to 5 (very much).

Cognitive impairment, psychosis, suicidality (screening). If cognitive functioning, current psychosis, and suicidality is questionable based on information provided by clinic staff, patient history, or research staff observation, to determine study eligibility, cognitive impairment will be assessed with the Mini Mental Status Exam (MMSE),²⁰ psychosis will be assessed with the Structured Clinical Interview for DSM-V (SCID) Psychotic screen,²¹ and suicidality will be assessed with the Columbia Suicide Severity Rating Scale (C-SSRS). The Mini-Mental Status Exam, MMSE is a widely used valid and reliable measure of cognitive functioning that assesses orientation to time and place, registration, attention and calculation, recall, language, Scores <24 indicate cognitive impairment. The SCID Psychotic Screen is a semi-structured clinical interview that assesses symptoms of psychotic disorders (e.g., delusions, hallucinations) based on the DSM-V criteria. The C-SSRS is a five-item reliably and valid measure that assesses suicidal ideation, plans, and intent.

Mental health history (Baseline), trauma (baseline, 8-weeks, and 16-weeks) and psychiatric symptoms and treatment (baseline, 8 weeks, 16 weeks). At baseline, history of mental illness and psychiatric treatment will be assessed. At each subsequent research visit, participants will be asked if they took any psychotropic medications or received any mental health counseling since their last visit. Trauma history will be assessed with the Brief Trauma Questionnaire (BTQ). ^{23,24} The BTQ is a 10-item self-report questionnaire that assesses traumatic experiences. At each research visit, symptoms of depression and anxiety will be evaluated with the Center for Epidemiologic Depress Scale and the Beck Anxiety Inventory. ²⁵

Physical health history (Baseline) and symptoms (Baseline, 8- and 16-- weeks) and medication (Baseline, 8- and 16-- weeks). At Baseline, history of illness such as HIV, cancer, heart disease, emphysema, asthma and other chronic conditions will be assessed. Daily health functioning will be evaluated at every research visit with the RAND 36-ltem Health Survey 1.0 (SF-36).²⁶ The reliability and validity of this self-report scale that measures overall health and ability to complete daily activities has been shown. Current pain and other medication (prescribed and over the counter) will be assessed at each research visit.

12

Version Number: 15, 2/2/2022 Protocol Number: Pro20190016877

PI Name: [name]

Protocol Title: Mindfulness Oriented Recovery Enhancement (MORE) as an Adjunct to Methadone Treatment RESERVED FOR IRB STAMP DO NOT MODIFY THIS SPACE

Savoring (Baseline, 8- and 16-- weeks). Savoring will be measured by the Savoring Beliefs Inventory (SBI), The SBI is a reliable and valid scale that consists of 6 items that assess individuals' perceptions of their ability to derive pleasure through anticipating upcoming positive events, savoring positive moments, and reminiscing about past positive experiences or the Momentary Savoring Scale,²⁷ which assesses the propensity to focus on the moment as a means of intensifying positive experience from naturally rewarding events.

Mindfulness practice. In addition to collecting EMA data we will assess mindfulness practice with the timeline follow-back. The timeline follow-back is a reliable and valid measure where participants are asked to recall and record events within a specified time period on a calendar.

MMT dose, MMT days of treatment, MMT services. This information will be abstracted from participants' clinic charts, with participants' consent.

The following cognitive tasks will be completed on a laptop computer or tablet. The online tasks will be administered through the Inquisit platform. Pre-developed Inquisit scripts exist for each computer task, and participants' encrypted task data will be housed on a secure server "using Secure Sockets Layer (SSL)", the same technology used by online shopping and banking web sites to protect sensitive information transmitted over the web" (https://www.millisecond.com/support/docs/v5/Inquisit.pdf). Each task will be scored within the Inquisit platform according to validated scoring methods.

Inhibitory control, Go-No Go Task (Baseline, 8-weeks): To assess inhibitory control, participants are asked to press the Spacebar on a computer when they see, on the computer screen, a green rectangle (=go) but refrain from pressing the Spacebar when they see a blue rectangle (=no go).²¹ The blue and green rectangles can be vertical or horizontal. The vertical rectangle has a high probability of being green (a go trial) and the horizontal rectangle has a high probability of being blue (a nogo trial). Participants get information about the orientation of the rectangle (=cue) shortly before the color of the rectangle is revealed. Mean reaction times will be derived from the Go/No-Go tasks.

Opioid/Natural Reward, Implicit Association Task (IAT; Baseline, 8-weeks): The IAT is a widely-used cognitivebehavioral paradigm that measures the strength of automatic (implicit) associations between concepts in people's minds relying on latency measures in a simple sorting task.²² Participants are asked to, on a computer, categorize attributes (e.g. "pleasant"; "unpleasant") and and target items (e.g "friends" vs. "pills") into predetermined categories via keystroke presses. The basic task is to press a left key (E) if an item (e.g. "pleasant") belongs to the category presented on the left (e.g. "Good") and to press the right key (I) if the word (e.g. " unpleasant ") belongs to the category ("Bad") presented on the right. For practice, participants sort items into the target categories "Opioids vs. Natural Reward" and the attribute categories "Good vs. Bad". For the test, participants are asked to sort categories into the paired/combined categories (e.g. "Natural Reward OR Good" on the left vs. "Opioid OR Bad" on the right). Pairings are reversed for a second test (e.g. "Opioid OR Good" on the left vs. "Natural Rewards OR Bad" on the right). Block order is counterbalanced by group number. A d-score will be derived from the implicit association task.

Precedence of Global Features in Visual Perception, Global Local Task (Baseline, 8-weeks): On a computer/tablet, participants are briefly presented with letter shapes (e.g. H or S) that are made up of little letter shapes (e.g. H or S). 23 Some of these letters have the same global (overall shape) and local (individual building shapes) letters (e.g. an H that consists of Hs), and some have different global and local letters (e.g. an H that consists of Ss). In the global condition participants are asked to respond to the global shape of the letter (e.g. press key H if the global

13

Version Number: 15, 2/2/2022 Protocol Number: Pro20190016877

PI Name: [name]

Protocol Title: Mindfulness Oriented Recovery Enhancement (MORE) as an Adjunct to Methadone Treatment

RESERVED FOR IRB STAMP DO NOT MODIFY THIS SPACE

shape of the letter is an H regardless of individual building blocks); in the local condition participants are asked to respond to the local shapes of the letter (e.g. press H if the local building elements are Hs regardless of overall shape). The number of errors during the last block of the global/local task will provide a shifting attention score.

Intervention implementation (Week 8). Number of sessions completed and missed will be assessed for each participant in both conditions. Reasons provided for missed sessions will also be recorded.

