Hypothesis 1.1. (**Primary Outcome**) MORE will result in longer duration of time to first opioid lapse and MMT dropout than TAU. We will use survival analysis (Kaplan Meier curves and marginal model analysis for multivariate survival data)³⁴ to test effects of MORE vs. TAU on time until first opioid lapse and MMT dropout—evidenced either on EMA, Timeline Follow-Back, urinalysis or medical records (whichever is first). Survival analysis will be run once, at 16 weeks post-baseline. Clustering within cohort will be adjusted in the multivariate marginal model analysis.³⁴ We will estimate the hazard ratios of opioid lapse and MMT dropout when comparing MORE with TAU, controlling for covariates.

Hypotheses 1.2 and 1.3 (Secondary Outcomes). MORE will result in more days of opioid abstinence (or less days of use) and a higher rate of biochemically-verified abstinence over time than TAU. Generalized linear mixed model (GLMM)³⁵ repeated measures analysis will be used. Specifically, identity link will be used for "number of abstinent days" as the dependent variable, and logit link will be used for "opioid abstinence (yes/no via urinalysis)" as the dependent variable. Days of use/abstinence will be assessed via EMA, number of drug use days since last visit and past 30 days, and the Timeline Follow-Back. In cases of conflicting findings across data sources, we will assume the highest number of days of use or lowest number of abstinent days recorded for that period. Analyses will include group (MORE vs. TAU), time, and group by time interactions as the fixed effects independent variables. Correlations among repeated measures and among subjects within cohorts will be modeled using nested random effects. Potential confounders that meet the p<0.10 criterion stated above will be entered as covariates. Linear contrasts will be constructed to test between-group differences in "days of use" or "days of abstinence" separately at each timepoint. In comparing days of use, if a substantial proportion of subjects do not use opioids, resulting in excessive zero days of use, we will use a two-part logistic/linear analysis model.^{36,37}

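### Time to first opioid lapse has no stated time zero, and MMT dropout and MMT days run from an undefined enrolment date, although randomisation waits for a clinic cohort to fill

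*Combined protocol and SAP*

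**What the plan says.** **Outcome definitions (section 1.9 B).** For the primary outcome: "Time until first opioid lapse assessed through ecological momentary assessment data and timeline follow-back". This names sources but no origin. For MMT dropout: "Time until dropout will be calculated from enrollment until last dose of methadone". For total MMT days: "Number of days will be calculated from enrollment until each follow-up timepoint". The text available for review does not define enrolment.

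**Primary analysis (section 6.1 A, Hypothesis 1.1).** The hypothesis labelled primary is "MORE will result in longer duration of time to first opioid lapse and MMT dropout than TAU". The event is the earliest evidence from EMA, Timeline Follow-Back, urinalysis or medical records, with no lower limit on its date. On timing: "Survival analysis will be run once, at 16 weeks post-baseline".

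**Day counts (section 6.1 A, Hypotheses 1.2–1.4).** Use days draw partly on "number of drug use days since last visit and past 30 days". Groups are compared by contrasts "separately at each timepoint", and MMT days follow the same strategy.

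**Randomisation (section 4.3).** Participants are randomised only after 10–18 have been recruited at a clinic, and the MORE group then begins.

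**The gap (sections 1.3 A and 4.8 B).** If baseline was more than 3 months before group start, the survey is repeated and paid for again. Neither section says that this resets an event clock.

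**The concern.** A time-to-event outcome cannot be computed without an origin. Here baseline and randomisation are separate dates by design, and the distance between them varies from person to person. Two analysts could build different primary datasets from the same text, and the choice could be left until outcome data are visible.

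If the clock starts at baseline or enrolment, time at risk and lapses from before allocation enter the comparison. Assignment cannot influence them, so they move the hazard ratio toward 1. Cutting follow-up at 16 weeks from baseline would also remove treated time from those who waited longest. Eligibility (section 4.2 D) does not require opioid abstinence, so use during the wait is to be expected.

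**Working it through.** **1. The clocks side by side**

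| Section | Statement, paraphrased | Points to |
|---|---|---|
| 1.9 B, outcome list | Lapse: sources only | No origin |
| 1.9 B, outcome list | Dropout and MMT days from enrolment | Undefined date |
| 1.9 B, EMA | EMA runs from baseline to week 16 | Baseline |
| 6.1 A | Survival analysis 16 weeks after baseline | Baseline, or only analysis timing |
| 1.3 A | Week 1 is the week of the first session | Group start |
| 1.3 C | Participation totals 16 weeks | Group start, if there was a wait |

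These agree only when the wait is nil. With a 91-day wait and no reset, day 112 from baseline is day 112 − 91 = 21 after group start, inside the 8-week course.

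**2. The plan's own figure.** Sections 1.5 and 6.1 B need 47 per group (HR 0.55, 80% power, two-sided 5%). Schoenfeld's formula gives 88 events. With a TAU median of 99 days, 1.5 years of accrual and 16 further weeks, the mean event probability is 0.806, so 88/0.806/2 ≈ 55 per group. Other readings reach 47 (for example Freedman's 94 events / 2), so I do not call it an error, and nothing below depends on it.

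**3. Reference case without a wait.** Take 92 per arm, 112 days each and no attrition, with λ = ln 2/99 = 0.0070 per day.
- TAU: 1 − exp(−112λ) = 0.544. MORE: 1 − exp(−0.55 × 112λ) = 0.350. Mean: 0.447.
- Events: 184 × 0.447 ≈ 82.
- Power: Φ(√82.2/2 × |ln 0.55| − 1.96) = 77% (76% by simulation).

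**4. Hand check with one fixed wait of 28 days (assumed), baseline clock.**
- Lapsed before randomisation: 1 − exp(−28λ) = 0.178, or 184 × 0.178 ≈ 33 events.
- Afterwards, to 16 weeks after group start: 184 × 0.822 × 0.447 ≈ 68. Total about 100, of which 33% precede randomisation.
- Event-weighted log HR: (67.6/100.3) × ln 0.55 = −0.403, so HR ≈ 0.67.
- Power: Φ(√100.3/2 × 0.403 − 1.96) = 52%. Stopping at day 112 from baseline gives HR 0.69 and power 42%.
- A 14-day wait gives HR 0.62 with power 64% and 59% respectively.

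**5. Variable waits, by simulation.** Hazard is λ before randomisation in both arms and 0.55λ in MORE afterwards; Cox model, 10,000 replicates. In sequential filling one cohort of size k fills at a time at 184/78 = 2.36 per week, so the mean wait is (k − 1)/(2 × 2.36): 1.9 weeks for k = 10 and 3.6 for k = 18. On the randomisation clock, people who used while waiting are assumed to use again after a mean of 30 or 7 days, equally in both arms.

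| Assumed wait | Baseline clock, to 16 weeks after group start: HR, power | Baseline clock, to day 112: HR, power | Randomisation clock: power (30 / 7 d) |
|---|---|---|---|
| Sequential, k = 10 | 0.609, 64.1% | 0.617, 58.2% | 65.5 / 64.3% |
| Sequential, k = 18 | 0.657, 53.2% | 0.673, 44.1% | 57.8 / 55.1% |
| Uniform 0–60 d | 0.670, 50.9% | 0.692, 39.0% | 54.4 / 50.5% |
| Uniform 0–90 d | 0.713, 41.3% | 0.753, 25.7% | 46.6 / 42.0% |

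Four clinics filling in parallel, with a repeat baseline resetting the clock after 91 days, fall in the same range (HR 0.62–0.70, power 37–61%).

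The gain from the randomisation clock is the last column minus an earlier one. Against the first it is −0.4 (50.5 − 50.9) to +5.3 (46.6 − 41.3). Against the second it is 6.1 (64.3 − 58.2) to 20.9 (46.6 − 25.7). Stratifying on use during the wait gives 64.7/65.6, 55.1/54.8, 51.1/51.8 and 41.3/40.5%, no consistent improvement; the lowest gain is then 40.5 − 41.3 = −0.8. Repeat runs moved results by a point or two (gains of −1 to +6 and 7 to 21), and the rounded ranges quoted elsewhere allow for that.

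**6. Dropout and MMT days.** Section 1.2 puts discontinuation at about 50% in 12 months. At that rate there are about 28 dropouts, with HR 0.55 and power 31–32%, with or without an event-free wait. Only if people who leave MMT while waiting are still randomised and counted does the HR move, to 0.60–0.69 (power about 20–28%). For MMT days the week-16 mean difference stays at 4.8 days, while the pooled SD rises from 24.0 to 25.5–35.4. The SD of the week-8 to week-16 change is 16.7 with every wait.

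**The case against.** The best reply is that group start is implied. Section 1.3 A anchors the visit calendar to the first session, participation and EMA are each said to last 16 weeks, and section 4.3 starts the group once participants are randomised. On that reading there is no dilution and the lapse part is a clarification. This is plausible, and it stands as a possible intention. It does not settle the text: the visit calendar is not tied to the survival outcomes, section 6.1 A speaks of baseline, and the one origin actually written down is enrolment.

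It is also fair that every wait is assumed. The documents give only the 3-month trigger, and filling one cohort at a time simplifies a design in which cohorts fill by site. The constant hazard from baseline is an assumption too.

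A reader might infer that a randomisation clock would restore the 76% of the no-wait case. It would not under these assumptions, because people who used while waiting tend to use again soon. The gain would be larger if MORE also slowed that re-use, but the documents give no basis for a figure.

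**Conclusion.** The point holds as a gap in definition with a conditional cost. The primary outcome has no stated origin, two companion outcomes start at an undefined date, the sections conflict, and no rule keeps pre-randomisation events out.

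If the baseline or enrolment wording is followed, the hazard ratio is about 0.61–0.76 instead of 0.55. Power is about 41–66% with follow-up to 16 weeks after group start and about 26–59% with a day-112 cut-off from baseline. A randomisation clock gives about 41–67%: a change of about −1 to +6 points in the first case and roughly 6 to 21 in the second. These figures rest on assumed waits, 184 participants, a 99-day TAU median, HR 0.55 after randomisation and no attrition.

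Two stronger inferences are not supported. One is that the gap favours MORE or inflates false positives: allocation follows the wait, so earlier events balance between arms in expectation. The other is that the plan commits the primary analysis to a baseline clock: it does not say so. Dropout is essentially unaffected unless people who leave MMT while waiting are still randomised. For MMT days only the variance of the by-timepoint contrasts rises.

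**What to change.** In both arms, set time zero for first lapse, MMT dropout and all day-count outcomes to the participant's randomisation date. Count only later events and days, and set the 112-day horizon and censoring from that date. Treat earlier EMA, Timeline Follow-Back, drug-screen and chart data as baseline information.

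Replace the enrolment origin in section 1.9 B and the baseline reference for the survival analysis in section 6.1 A accordingly. Reconcile sections 1.3 A, 1.3 C and the EMA window in 1.9 B with the same date. State how people who leave MMT before randomisation are handled.

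How people who used opioids during the wait enter the model is for the sponsor to pre-specify; adjusting for that use is optional. All of this should be settled before outcome data are examined.

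The cost is protocol and SAP wording, use of the randomisation date, and chart abstraction of MMT days from that date. No extra participants or visits are needed.
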